## Data analysis

The primary population for analysis will be those enrolled in the prospective cohort study comparing siponimod-exposed pregnancies with MS to the disease-matched cohort and the non-diseased cohort. Statistical analyses of those enrolled in the exposure series who do not meet the cohort study criteria will be descriptive only. All relevant exposure, outcome, and covariate data within each study group will be summarized using descriptive statistics annually. Means and standard deviations will be presented for continuous variables and frequencies and percentages will be presented for categorical variables. At the completion of the study, a final analysis with adjusted comparisons between cohort groups will be performed.

## Milestones

Planned dates of study milestones:

Start date of data collection: By December 2021

Last date of data collection: May 2032

Interim report submission: Annually beginning in August 2022 through August 2031

Final study report submission: May 2033

### 3 Amendments and updates

**Table 3-1 Study protocol amendments and updates**

Number	Date	Section of study protocol	Amendment or update	Reason
1.1	15 November 2022	Sections 2 and 7.2	Study settings have been amended to note that the comparator cohorts for this study (BAF312A2403) will be shared with the Kesimpta pregnancy registry OTIS sub-study. Accordingly, the inclusion and exclusion criteria for the comparator cohorts are amended to harmonize between both, Mayzent and Kesimpta – OTIS pregnancy registries.	Since the population under study (i.e. inclusion/exclusion criteria) are the same between this study (BAF312A2403) and the Kesimpta-OTIS pregnancy registry sub-study (OMB157G2403) and the two studies will run in parallel using the same design, the comparator cohorts will be common between both studies. The first 125 eligible pregnancies in the two comparator cohorts from the time of Kesimpta protocol approval will be included in both studies.

## 4 Milestones

**Table 4-1** Planned dates of study milestones

Milestone	Planned date
Start of data collection	By December 2021
End of data collection	May 2032
Interim reports	Annual submission beginning August 2022 through August 2031
Final study report submission	May 2033

## 5 Rationale and background

Siponimod is approved in the United States (US) for the treatment of relapsing forms of multiple sclerosis (MS) including clinically isolated syndrome, relapsing remitting disease, and active secondary progressive disease in adults and in Canada for the treatment of patients with secondary progressive multiple sclerosis (SPMS) with active disease evidenced by relapses or imaging features characteristic of multiple sclerosis inflammatory activity, to delay the progression of physical disability. Siponimod has also been approved in the European Union for the treatment of adult patients with secondary progressive multiple sclerosis (SPMS) with active disease evidenced by relapses or imaging features of inflammatory activity.

Siponimod is a sphingosine-1-phosphate (S1P) receptor modulator. Siponimod binds with high affinity to S1P receptors 1 and 5. Siponimod blocks the capacity of lymphocytes to egress from lymph nodes, reducing the number of lymphocytes in peripheral blood. The mechanism by which siponimod exerts therapeutic effects in multiple sclerosis is unknown, but may involve reduction of lymphocyte migration into the central nervous system ([Mayzent US PI](#)).

There are no adequate data on the developmental risk associated with the use of siponimod in pregnant women. Based on animal data and its mechanism of action, siponimod can cause fetal harm when administered to a pregnant woman. Reproductive and developmental studies in pregnant rats and rabbits have demonstrated siponimod-induced embryotoxicity and fetotoxicity in rats and rabbits and teratogenicity in rats. Increased incidences of post-implantation loss and fetal abnormalities (external, urogenital and skeletal) in rat and of embryo-fetal deaths, abortions and fetal variations (skeletal and visceral) in rabbit were observed following prenatal exposure to siponimod starting at a dose 2 times the exposure in humans at the highest recommended dose of 2 mg/day. In the US general population, the estimated background risk of major birth defects and miscarriage in clinically recognized pregnancies is 2%-4% and 15%-20%, respectively. The background risk of major birth defects and miscarriage for the indicated population is unknown ([Mayzent US PI](#)). Based on the pathophysiological considerations and the potential for drug exposure during pregnancy, an evaluation of the effects of drug exposure immediately before and during pregnancy is warranted. The Siponimod Pregnancy Registry will be conducted to fulfill the US Food and Drug Administration (FDA) post marketing requirement (PMR 3591-4) for siponimod .

The majority of individuals who are diagnosed with multiple sclerosis (MS) are women of childbearing age. Data suggest pregnancy course and birth outcomes among women with MS who deliver live born infants are generally similar to those of women without MS ([Tsui and Lee, 2011](#); [Nelson and Ostensen, 1997](#); [Jalkanen et al, 2010](#)). However, the use of immunomodulatory and immunosuppressive drugs to treat MS, as well as other potential confounding factors such as variation due to unplanned pregnancies (e.g., failure to take periconceptional folic acid supplements, discontinue alcohol and tobacco use, etc.) may have an impact on pregnancy outcomes. Thus, although maternal disease itself is not known to be a risk, it has not been comprehensively studied. In the context of a medication exposure, it is critical to control for the contribution of the maternal disease as well as comorbidities and other exposures that may contribute to pregnancy risk.

## 6 Research question and objectives

The purpose of the Siponimod Pregnancy Exposure Registry is to evaluate the effect of siponimod exposure on rates of pregnancy and infant outcomes in exposed pregnancies compared to unexposed disease-matched and healthy unexposed pregnancies. The lack of human fetal safety data for siponimod makes such a monitoring system an important component of epidemiologic research on the safety of this drug.

The primary objective is to estimate and compare the prevalence of major structural defects in siponimod exposed pregnant women versus 1) disease-matched pregnant women not exposed to siponimod, and 2) healthy pregnant women.

The primary objective will be evaluated among i) pregnancies ending in at least one live birth, and ii) pregnancies ending in at least one live birth, spontaneous abortion, still birth or termination of pregnancy

Secondary objectives are to estimate and compare the prevalence of selected adverse pregnancy and infant outcomes in siponimod-exposed pregnant women versus 1) disease-matched pregnant women not exposed to siponimod, and 2) healthy pregnant women.

Mayzent exposure is defined as exposure to siponimod any time from the 4th days post the first day of LMP prior to conception up to and including the end of pregnancy.

- The primary outcome of the study is major structural defects.
- The secondary outcomes of the study are:
  - Spontaneous abortion/miscarriage
  - Stillbirth
  - Elective termination
  - Preterm delivery
  - Preeclampsia / eclampsia
  - Pattern of 3 or more minor structural defects
  - Small for gestational age
  - Postnatal growth small for age at approximately one year of age
  - Developmental performance at approximately one year of age
  - Serious or opportunistic infections in the first year of life.

## 7 Research methods

### 7.1 Study design

This study will utilize a prospective, observational, exposure cohort design to examine pregnancy and infant outcomes in women and infants who are exposed to siponimod during pregnancy to treat MS. The prevalence of outcomes in women exposed to siponimod and their infants will be compared to those observed in two unexposed comparator groups: a disease-matched comparison group of women who have not used siponimod during pregnancy (from the 4th days post the first day of the LMP prior to conception and throughout pregnancy) but have been diagnosed with MS (disease-matched unexposed comparison group), and a comparison group of healthy women who have no diagnosis of MS, have not had exposure to a

known human teratogen, and have not taken siponimod in pregnancy (healthy comparison group). Although the Registry will follow-up on all pregnancies exposed to siponimod (exposure series), the core of the Registry will be a prospective, observational cohort study designed to ascertain and follow up on pregnancy exposures to siponimod that meet the eligibility criteria and to compare these to the above two unexposed comparator groups. All subjects will be recruited via voluntary participant registration following informed consent by the pregnant woman for her participation. Subjects may withdraw from the study at any time.

An interim feasibility assessment will be performed after three years from registry initiation to ensure that the study can meet the sample size requirements within a reasonable timeframe to address the scientific question of interest (i.e. within 10 years from registry initiation). This interim feasibility assessment will consider data from this Registry and all available data sources such as real-world evidence studies, pharmacovigilance and marketing.

## 7.2 Setting

The Pregnancy Exposure Registry is sponsored by Novartis (referred later as “Sponsor”) and conducted by the Organization of Teratology Information Specialists (OTIS) Research Group, a network of university and health department based telephone information centers serving pregnant women and healthcare providers throughout North America ([Leen-Mitchell et al, 2000](#)). These services receive spontaneous telephone inquiries from women and healthcare providers about the safety or risk associated with environmental exposures in pregnancy, including medications. Trained Teratogen Information Specialists at each site provide appropriate risk assessment and referral for all patient and healthcare provider callers free of charge. These services also provide a basis for collaborative research such as this Registry. Thus, individual Teratogen Information Services located throughout the US and Canada will serve as a source of referrals not only for siponimod-exposed pregnancies but also for similarly ascertained disease-matched comparison pregnant women who have not used siponimod in pregnancy and similarly-ascertained healthy pregnant women who have no diagnosis of the approved indication, have not had exposure to a known human teratogen, and have not taken siponimod in pregnancy.

Organization of Teratology Information Specialists member services receive over 70,000 teratogen information inquiries per year, therefore OTIS members constitute a major source of identification and recruitment of exposed women and appropriate comparison women. Once women are in contact with the OTIS Research Center, enrollment in the Registry is voluntary and requires informed consent of the pregnant woman. The Registry encourages enrollment as early in the pregnancy as possible, before any prenatal testing results are known. This is accomplished by encouraging clinicians to refer patients, and patients who contact an OTIS service or who self-refer, to enroll upon first positive pregnancy test. These efforts reduce possible bias based on prior knowledge of a normal or abnormal ultrasound and allow for better estimation of risk of spontaneous abortion.

The study population includes pregnant women who reside in the US or Canada with siponimod-exposure for the approved indication, and 2 comparison groups without siponimod exposure during pregnancy (1 disease-matched unexposed comparison group, and 1 healthy unexposed comparison group). Since the population under study (i.e. inclusion/exclusion criteria) are the same between this study (BAF312A2403) and the Kesimpta-OTIS pregnancy

registry sub-study (OMB157G2403) and the two studies will run in parallel using the same design, the comparator cohorts will be common between both studies. The first 125 pregnancies in the two comparison groups from the time of Kesimpta protocol (OMB157G2403) approval will be eligible for inclusion in both studies (i.e., the current study and the Kesimpta-OTIS pregnancy registry sub-study).

Based on use of multiple methods for identification and recruitment of exposed women, and the previous recruitment experience of the existing OTIS studies, the investigators have projected that approximately 17-18 pregnant women with exposure to siponimod could be enrolled in the Registry each year, although the true number of exposed pregnancies potentially available for enrollment in the Registry cannot be known at this time.

### **7.2.1 Study period**

The study is planned for about 10.5 years from the enrollment of the first patient in (FPI) until study completion. There will be 7 years of active recruitment, with an annual interim report reviewed by the Scientific Advisory Board each year. The final report with statistical analysis according to the statistical analysis plan (SAP) will be prepared at the end of the study.

Pregnant women will be followed throughout their pregnancy and pregnancy outcome information will be collected. Live born infants will be followed through one year of age.

### **7.2.2 Eligibility criteria**

The prospective cohort study will enroll pregnant women in three cohorts. Eligibility for the cohort study includes the following:

- Residence in the U.S. or Canada at the time of enrollment
- Currently pregnant women
- Verbal consent to participate in the study

#### **7.2.2.1 Inclusion criteria for core prospective study**

Participants must meet all the criteria listed under the respective cohorts to enroll in that particular cohort of the registry:

#### **Cohort 1: Siponimod-Exposed Cohort**

1. Pregnant women
2. Diagnosed with MS, with the indication validated by medical records when possible
3. Exposure to siponimod for the treatment of MS, for any number of days, at any dose, and at any time from the 4th day post the first day of LMP prior to conception up to and including the end of pregnancy
4. Agree to the conditions and requirements of the study including the interview schedule, release of medical records, the dysmorphology examination of live born infants, and the Ages and Stages Questionnaire (ASQ) in live born children

#### **Cohort 2: Disease-Matched Comparison Cohort (Comparison Group 1)**

1. Pregnant women

2. Diagnosed with MS, with the indication validated by medical records when possible
3. May or may not have taken another medication for MS in the current pregnancy (see exclusionary medications [Section 7.2.2.2](#))
4. Agree to the conditions and requirements of the study including the interview schedule, release of medical records, the dysmorphology examination of live born infants, and the ASQ in live born children

### **Cohort 3: Healthy Comparison Cohort (Comparison Group 2):**

1. Pregnant women
2. Agree to the conditions and requirements of the study including the interview schedule, release of medical records, the dysmorphology examination of live born infants, and the ASQ in live born children

#### **7.2.2.2 Exclusion criteria for the core prospective study**

Women meeting any of the following criteria will be excluded from the cohort study:

#### **Cohort 1: Siponimod-Exposed Cohort**

1. Women who have enrolled in the siponimod cohort study with a previous pregnancy
2. Women who have used siponimod for an indication other than a currently approved indication
3. Women with exposure to any of the following medications within 5 half-lives prior to conception:
  - Cladribine (Mavenclad)
    - Based on the US label, animal studies indicate that there is positive evidence of teratogenicity for Cladribine
  - All other S1P modulators including fingolimod (Gilenya), ozanimod, etc.
    - S1P modulators are in the same class of drug as siponimod
  - Teriflunomide (Aubagio)
    - The teratogenicity of teriflunomide is unknown and currently under investigation
  - Other anti-CD20 monoclonal antibody: same class as Kesimpta
  - New medications (marketed after 2020) indicated for the treatment of MS will be evaluated for inclusion/exclusion criteria as the study progresses.
4. Retrospective enrollment after the outcome of pregnancy is known (i.e. the pregnancy has ended prior to enrollment)
5. Results of a diagnostic test are positive for a major structural defect prior to enrollment ([Section 7.7.2.3](#)). However, women who have had any normal or abnormal prenatal screening or diagnostic test prior to enrollment are eligible as long as the test result does not indicate a major structural defect.

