### Rationale and background

Mayzent (siponimod) is a selective sphingosine 1 - phosphate receptor modulator that causes lymphocyte sequestration in the lymph nodes and presumably reduced migration to the central nervous system (Behrangi et al 2019). Mayzent is approved in the United States (US) for the

treatment of relapsing forms of multiple sclerosis (MS) including clinically isolated syndrome, relapsing remitting disease, and active secondary progressive disease in adults and in Canada for the treatment of patients with secondary progressive multiple sclerosis (SPMS) with active disease evidenced by relapses or imaging features characteristic of multiple sclerosis inflammatory activity, to delay the progression of physical disability.

Mayzent has been found to have a teratogenic and embryotoxic effect in studies in rats. Furthermore, the receptor family modulated by Mayzent (sphingosine 1 - phosphate receptor) is known to be involved in vascular formation during embryogenesis. Data on Mayzent exposure during pregnancy in the clinical program is very limited and it is not known whether Mayzent can affect pregnancy and infant outcomes in humans. Since it takes approximately 10 days to eliminate Mayzent from the body after stopping treatment, any drug administration on or after the 4th day post the first day of the last menstrual period (LMP) and up to the end of pregnancy may expose the fetus to the drug. This exposure period is derived by taking the conception date (operationalized here as first day of LMP+14 days) as the start of pregnancy and accounting for the above stated Mayzent elimination period (10 days). Based on the pathophysiological considerations and the potential for drug exposure during pregnancy, an evaluation of the effects of drug exposure immediately before and during pregnancy is warranted.

Reference is made to the approval letter for Mayzent dated March 26, 2019 and specifically the post-marketing requirement (PMR) 3591-4. The Mayzent Pregnancy Registry will be conducted to fulfill PMR 3591-4

The Pregnancy Exposure Registry is sponsored by Novartis and conducted by the Organization of Teratology Information Specialists (OTIS) Research Group. It is administered by investigators at the coordinating site located at the [REDACTED].

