### **Cohort 2: Disease-Matched Comparison Cohort (Comparison Group 1):**

1. Exposure to siponimod any time from the 4th day post the first day of LMP prior to conception up to and including end of pregnancy
2. Women with exposure to any of the following medications within 5 half-lives of conception:
  - Cladribine (Mavenclad)
  - SIP modulators
  - Teriflunomide (Aubagio)
  - Anti CD-20 monoclonal antibody

New medications (marketed after 2020) indicated for the treatment of MS will be evaluated for inclusion/exclusion criteria as the study progresses.

3. Women who have enrolled in the siponimod cohort or OMB157G2403 Kesimpta cohort with a previous pregnancy
4. Retrospective enrollment after the outcome of pregnancy is known (i.e. the pregnancy has ended prior to enrollment)
5. Results of a diagnostic test are positive for a major structural defect prior to enrollment. However, women who have had any normal or abnormal prenatal screening or diagnostic test prior to enrollment are eligible as long as the test result does not indicate a major structural defect.

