### **Cohort 3: Healthy Comparison Cohort (Comparison Group 2):**

1. Exposure to Kesimpta 166 days before or to siponimod any time from the 4th day post first day of LMP prior to conception up to and including end of pregnancy
2. Women who have a diagnosis of a MS or a siponimod approved indication
3. Women who have a current diagnosis of any autoimmune disease
4. Women who have first contact with the project after prenatal diagnosis of any major structural defect
5. Women who have enrolled in the siponimod cohort or Kesimpta cohort study with a previous pregnancy
6. Women treated with Mayzent or Kesimpta for non-MS indication
7. Retrospective enrollment after the outcome of pregnancy is known (i.e. the pregnancy has ended prior to enrollment)
8. Results of a diagnostic test are positive for a major structural defect prior to enrollment. However, women who have had any normal or abnormal prenatal screening or diagnostic test prior to enrollment are eligible as long as the test result does not indicate a major structural defect.
9. Women exposed to a known human teratogen during pregnancy as confirmed by the OTIS Research Center

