- **Analysis subset:** for the primary outcome of major structural defects, the etiologically relevant window, with rare exceptions, is any exposure in the first trimester and the analysis subset in cohort 1 will be restricted to those with exposure to at least 1 dose of Mayzent from the 4th day post first day of to LMP prior to conception through the end of the first trimester. It is possible that some pregnant women in Cohort 1 could have exposure to Mayzent limited to the second or third trimester, and these would be considered separately. Duration and gestational timing of exposure to siponimod will also be considered.
- **Time period for identification:** major structural defects identified up to one year of age by the mother or the healthcare provider/medical record will be included in the primary analysis. Defects identified after that time frame will be described and considered separately.
- **Confirmation of defects:** independent confirmation of certain defects will be required. For example, a heart murmur thought to represent a ventricular septal defect

prior to 1 year of age will be included if it is confirmed as a heart defect by cardiac ultrasound. Similarly, a midline cutaneous marker at L2-L3 noted will be included as occult spinal dysraphism only if confirmed by appropriate imaging studies.

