#### 7.7.3.1.1 Analyses of the primary outcome

The primary outcome of interest, i.e. major structural defects, will be estimated in each cohort as a proportion (95% CI) using two denominators i) pregnancies ending in at least one live born infant and ii) pregnancies ending in at least one live born infant, stillborn, spontaneous abortion or elective termination. Data will also be presented by gestational timing of exposure.

For the primary endpoint, the exposure of interest is siponimod exposure at any time from the 4th day post the first day of the LMP prior to conception to the end of the first trimester, whether or not there is continued exposure to siponimod in the second or third trimesters. The primary comparison will be the rate of major structural defects between the siponimod-exposed group and comparison group 1 (disease-matched comparison group) among pregnancies resulting in at least one live born infant. A point estimate of the crude (i.e. unadjusted) risk ratio (RR) of the siponimod-exposed group versus comparison group 1, as well as its 95% confidence interval (CI) will be computed.

The same analysis will be repeated using the second numerator and denominator encompassing pregnancies ending in at least one live births, stillbirth, spontaneous abortion or elective termination, but excluding those lost-to-follow-up.

Due to the observational nature of the study, the above crude estimate of RR will be further adjusted for potential confounders (Rosenbaum, 2002), provided that there are sufficient numbers of events. A complete list of potential confounders, which includes but not limited to the baseline characteristics, will be provided in the SAP for each outcome prior to the final analysis, based on scientific knowledge including literature review.

As a primary approach, following Levenson and Yue, 2013, all potential confounders will be accounted for in the propensity score model.

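### The exclusion window for other MS drugs is worded differently in Cohorts 1 and 2, and in neither is it stated to run through the first trimester

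*Protocol*

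**What the plan says.** The list of excluded MS drugs appears twice in Protocol section 7.2.2.2, with different windows:

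- Cohort 1 (siponimod-exposed): "Women with exposure to any of the following medications within 5 half-lives prior to conception".
- Cohort 2 (disease-matched): "Women with exposure to any of the following medications within 5 half-lives of conception".

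Both lists name cladribine, S1P modulators (for Cohort 1, those other than siponimod), teriflunomide and anti-CD20 antibodies. Neither mentions use during pregnancy, and no half-lives are given.

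Other passages bear on how the windows should be read:

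- In the same Cohort 2 list, siponimod is barred from the fourth "day post the first day of LMP prior to conception up to and including end of pregnancy".
- Cohort 2 inclusion criterion 3 (section 7.2.2.1) reads "May or may not have taken another medication for MS in the current pregnancy (see exclusionary medications" and points to section 7.2.2.2.
- The only teratogen exclusion tied to use in pregnancy is in Cohort 3: "Women exposed to a known human teratogen during pregnancy as confirmed by the OTIS Research Center".
- The Abstract fixes conception by "taking the conception date (operationalized here as first day of LMP+14 days) as the start of pregnancy".
- For major structural defects, section 7.7.2.2 says that "the etiologically relevant window, with rare exceptions, is any exposure in the first trimester".
- Section 7.7.3.1.1 states: "The primary comparison will be the rate of major structural defects between the siponimod-exposed group and comparison group 1".

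**The concern.** The Cohort 1 list gives its reasons: animal evidence of teratogenicity (cladribine), unknown teratogenicity (teriflunomide), or membership of the same class as siponimod or Kesimpta. Those reasons apply to use during organogenesis at least as much as to residue from earlier use. Yet the Cohort 1 rule, followed as written, removes the earlier use and admits a woman who first takes a listed drug at, say, six weeks of gestation. Cohort 2 may admit such a woman too, depending on how one word is read.

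These two cohorts form the primary comparison. Such use in Cohort 2 would raise the comparator defect rate and pull the risk ratio toward 1, which in a safety study tends to hide harm. Such use in Cohort 1 would add defects not caused by siponimod. With recruitment planned over seven years, an unclear window also invites eligibility decisions that differ between cohorts or over time.

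**Working it through.** The protocol gives no figure on this point to reproduce. The check sets the criteria side by side, then does two short calculations.

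**Step 1. What each criterion excludes.**

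| Use of a listed drug | Cohort 1 | Cohort 2, *of* read as before | Cohort 2, *of* read as either side |
|---|---|---|---|
| Within 5 half-lives before conception, including continuous use | excluded | excluded | excluded |
| First taken within 5 half-lives after conception | not excluded | not excluded | excluded |
| First taken later in the first trimester | not excluded | not excluded | not excluded |

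A woman whose last pre-conception dose lies more than five half-lives back, and who is re-dosed after conception, is treated like a new starter. No other criterion for Cohort 1 or 2 bars these drugs after conception.

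**Step 2. Reach of a two-sided Cohort 2 window.** For a half-life of h days it ends 5h days after conception. The protocol does not define the end of the first trimester, so it is assumed here to fall 10 to 12 weeks (70 to 84 days) after conception. Full cover needs 5h ≥ 70 to 84, so h ≥ 14 to 16.8 days. For shorter half-lives part of the trimester is left open.

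**Step 3. Size, by illustration.** Inputs from Table 7-4: 231 live-birth pregnancies per group, 3% comparator rate, risk ratio 3.0. Expected comparator defects are 231 × 0.03 = 6.93. Let a share q of one cohort have first-trimester use of a listed drug, with k times the baseline defect risk. Both q and k are assumptions with no source in the protocol.

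- Cohort 2 only: comparator rate = 3% × (1 + q(k − 1)); extra defects = 6.93 × q(k − 1); observed risk ratio = 3.0 / (1 + q(k − 1)).
- Cohort 1 only, with no siponimod effect: observed risk ratio = 1 + q(k − 1).

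| q | k | Comparator rate | Extra defects in Cohort 2 | True 3.0 seen as | True 1.0 seen as |
|---|---|---|---|---|---|
| 2% | 2 | 3.06% | 0.14 | 2.94 | 1.02 |
| 5% | 3 | 3.30% | 0.69 | 2.73 | 1.10 |
| 10% | 5 | 4.20% | 2.77 | 2.14 | 1.40 |

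The last row is a deliberately extreme case. For scale, the crude 95% interval around a risk ratio of 3.0 with 20.79 and 6.93 expected events has log standard error √(1/20.79 − 1/231 + 1/6.93 − 1/231) = 0.429. The interval is exp(1.099 ± 1.96 × 0.429), about 1.3 to 7.0.

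**The case against.** The case that this matters little has five parts.

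1. *Intent.* Cohort 2 inclusion criterion 3 refers to the exclusion list when speaking of MS drugs taken in the current pregnancy, so the list was probably meant to govern such use. This stands as evidence of intent and makes loose drafting more likely than a deliberate choice to admit these drugs. It does not supply the missing end date, and Cohort 1 has no such cross-reference.
2. *Different windows.* A reader might infer both that the two arms use different windows and that Cohort 2 excludes no post-conception start. Both cannot hold in full. If *of* means before, the windows match and only the wording differs. If it means either side, some post-conception starts are excluded in Cohort 2. The documents do not settle which.
3. *The protocol's own drugs.* It is tempting to say that the protocol gives both siponimod and Kesimpta a full-pregnancy window but denies one to the confounding drugs. For the primary comparator this is true of siponimod only; the Kesimpta window appears in Cohort 3 alone.
4. *Adjustment.* Known-teratogen exposure is a listed confounder, with an exclusion analysis if events are too few (section 7.7.3.1.1). Medication and treatment history are also listed, and all potential confounders enter the propensity score, with the full list left to the SAP. This partly stands. The teratogen provisions are limited to known human teratogens, a class that the listed drugs need not meet on the protocol's own description. The other items may reduce the bias but are not stated to capture new starts in pregnancy. Adjustment is also conditional on sufficient events, and about seven are expected in Cohort 2.
5. *Size.* Under the moderate assumptions Cohort 2 gains less than one defect, well inside sampling error, and contamination of both arms would partly offset. This stands.

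**Conclusion.** The point holds as a gap and inconsistency in the eligibility wording. The Cohort 1 window literally ends at conception, the Cohort 2 window is ambiguous, and neither is stated to run through the protocol's own etiologic window. It concerns only women who start or are re-dosed with a listed drug after conception, since use within five half-lives before conception is already excluded in both cohorts.

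The likely effect is small: a true risk ratio of 3.0 read as 2.94 to 2.73, or a null read as 1.02 to 1.10, for assumed shares of 2 to 5% and relative risks of 2 to 3. A reader might infer that the primary comparison is materially biased toward no effect. The documents do not support that: they give no share of such use, no half-lives and no defect risks, and bias in the two arms runs in opposite directions. The change is still worth making because it removes an avoidable source of bias and of inconsistent eligibility decisions at little cost.

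**What to change.** Reconcile Cohort 2 inclusion criterion 3 (section 7.2.2.1) with the Cohort 1 and Cohort 2 drug lists (section 7.2.2.2). Use one identically worded window in both cohorts, with an explicit start and an explicit end. For the primary-outcome analysis subset in section 7.7.2.2, apply it from the stated pre-conception start through the end of the first trimester, identically in Cohorts 1 and 2, and define when the first trimester ends.

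Placing the rule in the analysis subset matters because women are expected to enroll at 7 to 10 weeks post-LMP on average, so some first-trimester starts will occur after enrollment. Extending the exclusion to the end of pregnancy is not needed for this purpose. It would drop women for exposure outside the etiologic window in a registry that already expects poor enrollment.

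The cost is a sentence in each list and one in the analysis subset, plus the loss of the few women who start a listed drug in the first trimester. Siponimod-exposed women removed this way can be followed in the exposure series. No new data are needed: medication exposures are already collected at the interviews and in the pregnancy diary.
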